Secondary Objectives:	
1. To identify imaging biomarkers that are associated with the probability of any post-treatment improvement of FEV1 of 5% or more2. To identify imaging biomarkers that are associated with the probability of any post-treatment reduction in maintenance OCS use							
Exploratory Objectives:	
1. To identify imaging biomarkers that are associated with the probability of any reduction in pre-treatment baseline hospitalizations for asthma2. To identify imaging biomarkers that are associated with the probability of any post-treatment improvement in ACT score3. To identify imaging biomarkers that are associated with the probability of any subjective post-treatment reduction in symptoms described clinically							
Endpoints:	Primary Endpoint:	Determine the cutoff value in chest wall muscle size/quality that optimally classifies patients that had and did not have any reduction in pre-treatment baseline exacerbation frequency (binary). Alternative (continuous): determine the strength of the linear/non-linear relationship						

	between continuous chest wall muscle size/quality and continuous change in exacerbation frequency
Secondary Endpoints:	
 1. Determine individual and combinations of body composition measures (phenotypes) associated with a 5% or greater improvement in FEV1 when compared to baseline FEV1 2. Determine individual and combinations of body composition measures associated with any reduction in maintenance OCS use when compared to baseline OCS use
Exploratory Endpoints:	
These endpoints may be limited in scope of analysis by the sample size within each of the outcome groups.
 
 1. Determine individual and combinations of body composition measures associated with any reduction in hospitalizations when compared to baseline hospitalizations 2. Determine individual and combinations of body composition measures associated with any improvement in ACT score when compared to baseline ACT score 3. Determine individual and combinations of body composition measures associated with any subjective improvement of symptoms when compared to baseline symptoms

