3 OBJECTIVES AND ENDPOINTS

OBJECTIVES	ENDPOINTS	JUSTIFICATION FOR ENDPOINTS
Primary		
To identify imaging biomarkers that are associated with the probability of any reduction in pre-treatment baseline exacerbation frequency in a severe asthma population on biologics	Any reduction in exacerbations when compared to baseline exacerbations	Reduction in exacerbations is the primary clinical endpoint used in phase III trials to get many of the biologics used in asthma approved. Finding imaging biomarkers that associate with and possibly predict which patients will not have a reduction in exacerbations would be critical information for clinicians considering biologic initiation.
Secondary		
To identify imaging biomarkers that are associated with the probability of any post-treatment improvement of FEV1 of 5% or more	5% or greater improvement in FEV1 when compared to baseline FEV1	FEV1 is an important measure of lung function for patients with asthma, and any imaging biomarkers that predict a failure to improve this measure would be clinically useful.
To identify imaging biomarkers that are associated with the probability of any post-treatment reduction in maintenance OCS use	Any reduction in maintenance OCS use when compared to baseline OCS use	OCS are associated with multiple comorbidities, especially in the asthma population. Multiple phase III studies are currently underway to study maintenance OCS reduction in asthma due to this clinical concern and is a common reason for initiating biologics. Any imaging biomarkers that predict a failure to wean OCS after biologic initiation would be clinically useful.
Exploratory		
To identify imaging biomarkers that are associated with the probability of any reduction in pre-treatment baseline hospitalizations for asthma	Any reduction in hospitalizations when compared to baseline hospitalizations	Hospitalizations represent the most severe form of exacerbation and being able to find imaging biomarkers that associate with no improvement in hospitalizations would be clinically significant.
To identify imaging biomarkers that are associated with the probability of any post-treatment improvement in ACT score	Any improvement in ACT score when compared to baseline ACT score	Failure to improve symptoms after biologic initiation is a clinically frustrating scenario and finding imaging biomarkers that can predict this would be important for biologic initiation.

OBJECTIVES	ENDPOINTS	JUSTIFICATION FOR ENDPOINTS

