4 STUDY DESIGN

4.1 OVERALL DESIGN

Over an 18-month period we plan to conduct our study in 3 parts as identified in the study timeline table above.

University of Michigan Cohort Discovery, Database Construction, and Baseline Analysis

We plan to utilize existing data analytic tools at the University of Michigan to search the EMR for eligible patients to include in a retrospective cohort as identified by the inclusion criteria in section 5. We estimate that approximately 300 subjects will meet our initial criteria based on a preliminary search. We will then abstract all available clinical information from the EMR, de-identify it (with coded key stored in a separate, secured location), and enter the resulting coded data into a database. Up to 2 years prior to biologic initiation or CT scan (whichever is earlier) and all post-biologic therapy information will be included. Clinical information we will abstract will include demographic information, heights, weights, comorbid illnesses (coded as malignancy, coronary artery disease, diabetes, stroke/TIA, cirrhosis, and CKD), non-biologic asthma medication dosage and frequency of use (OCS, ICS, SABA, LAMA, LABA, montelukast, zileuton, and theophylline), asthma biologic agent (benralizumab, reslizumab, mepolizumab, omalizumab, and dupilumab) start and (if applicable) end dates as well as reason for end date (coded as ineffective, cost, intolerance/allergy, non-compliance, lost to follow-up, and other), FeNO, ACT scores, serum and sputum eosinophil counts, IgE, pulmonary function test parameters (% predicted), hospital/emergency room/urgent care/unscheduled office visits and phone call encounters for asthma or breathing-related complaints, and subjective clinician assessment of asthma control (independently graded by 2 different clinicians interpretation of EMR data). Each subject will also be assigned a phenotype by the Severe Asthma Research Program criteria¹⁵. If a majority of subjects are missing post-bronchodilator data and unable to be clustered by these criteria, we will instead assign adopted clusters from this paper as follows: Cluster 3-Normal FEV1 ($\geq 68\%$ of predicted), eosinophils (< 200 cells/ μL), FeNO (< 25 ppb), and IgE (< 200 UI/ml) and no evidence of atopy; Cluster 4-Reduced FEV1 ($\leq 68\%$ of predicted) with abnormal elevation of eosinophils, FeNO, or IgE and/or evidence of atopy; Cluster 5--Reduced FEV1 ($\leq 68\%$ of predicted) with normal eosinophils, FeNO, or IgE and no evidence of atopy. We do not expect to have any Cluster 1 or 2 patients in our study but will assign them accordingly if present. We will perform similar abstraction procedures for approximately 200 patients in the University of Calgary cohort, and label the data with a tag for this cohort for analytical purposes.

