
For the purposes of our analysis, we will define baseline measurements as the average of all data obtained in the year prior to biologic initiation or, if only one clinical encounter (defined as an office or emergency room visit) is available in this time period, then the average of the 2 clinical encounters immediately prior to biologic initiation will be used with the time frame noted in the database. In order to assess our primary and secondary outcomes we will use the average of all data from 4 to 18 months after biologic initiation or, if only one clinical encounter is available in this time period, the average of the 2 clinical encounters closest to, but not before 4 months after, biologic initiation. If a second biologic is introduced or the initial biologic choice is

changed, we will use all clinical data prior to the change, even if it is before 4 months of use, then follow the above steps to collect new outcome data on the new drug (see **Figure 4**).

[figure not shown]

Figure 4. Baseline and Response Clinical Data Plan.

Since our interest is primarily in finding the ~15% of patients who do not respond to biologics, we have chosen to include partial and complete responders together in our endpoints in order to isolate the non-responder population. Table 1 below will represent the dichotomization of responders and non-responders for each endpoint using the baseline and post-biologic data as detailed above. An exacerbation will be defined as any hospitalization, urgent care, emergency room, or unscheduled office visit for asthma or a breathing-related complaint or a temporary increase of OCS or ICS dosing for 3 or more days with the intent of the increase to treat acute symptoms. For clinician response, clinical encounter notes will be read and interpreted by 2 independent physicians and graded as detailed in the table. Upon completion of all data abstraction the patient will be de-identified as described in data handling below.

	Responder	Non-responder
Exacerbations	Any decrease from baseline	No change from baseline
Hospitalizations	Any decrease from baseline	No change from baseline
Maintenance oral corticosteroid (OCS) use	Any decrease from baseline	No change from baseline

Change in FEV1	$\geq 5\%$ improvement from baseline	<5% improvement from baseline
ACT score	≥ 1 -point improvement from baseline	No change from baseline
Clinician impression of response to therapy	Any improvement in symptoms from baseline	No change from baseline

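### The secondary FEV1 endpoint is analysed only as a yes/no cut at 5% improvement; a pre-specified continuous analysis beside it would be a cheap improvement

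*Combined protocol and SAP*

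**What the plan says.** The synopsis gives the first secondary endpoint as "Determine individual and combinations of body composition measures (phenotypes) associated with a 5% or greater improvement in FEV1 when compared to baseline FEV1". The objectives table in section 3 repeats it as "5% or greater improvement in FEV1 when compared to baseline FEV1". Section 4.1 states that "Table 1 below will represent the dichotomization of responders and non-responders for each endpoint", and the FEV1 row of that table separates 5% or more from less than 5%. Maintenance OCS ("Any reduction in maintenance OCS use when compared to baseline OCS use") and the exploratory ACT endpoint ("Any improvement in ACT score when compared to baseline ACT score") are also defined only as responder classes.

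The data behind the FEV1 cut are continuous: the abstraction list in section 4.1 includes "pulmonary function test parameters (% predicted". For the primary endpoint only, the synopsis adds an alternative that measures the relationship "between continuous chest wall muscle size/quality and continuous change in exacerbation frequency".

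Section 4.1 gives a reason for the cuts. The interest is mainly in the roughly 15% who do not respond, so "we have chosen to include partial and complete responders together in our endpoints in order to isolate the non-responder population". Section 3 explains why FEV1 matters but not why 5% is the threshold. Section 6.3 models a probability of response by elastic net, random forest and gradient boosting, and names no continuous outcome.

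**The concern.** Under the 5% cut, a patient who gains 4.9% counts the same as one who loses 20%, and a patient who gains 5.1% counts the same as one who gains 40%. The study looks for markers among a very large set of CT measures, in about 300 Michigan patients with a check in about 200 from Calgary. Section 3 also expects some endpoint data to be missing, so the analysed numbers may be smaller. In that setting, reducing a measured change to two classes can hide a marker that is graded with FEV1 change. The plan accepts a continuous reading for exacerbations but does not extend it to FEV1, where the measurement is more naturally continuous.

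**Working it through.** **No figure to reproduce.** The documents contain no power calculation. The 300 in section 4.1 is a count from a preliminary search.

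**Inputs from the documents.** n = 300 (Michigan) and n = 200 (Calgary), both approximate and taken before missing outcomes; the cut at 5%.

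**Assumed inputs.** Two-sided alpha of 0.05 for one marker; marker-change correlation r from 0.15 to 0.30; bivariate normal marker and FEV1 change; proportion p in the smaller outcome group of 0.50, 0.30 or 0.15. The documents give none of these for FEV1.

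**Step 1: information kept.** Cutting a normal outcome multiplies r by f = φ(z_p)/√(p(1−p)). The share of information kept is f².

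- p = 0.50: f = 0.3989/0.5000 = 0.798, f² = 0.64; 300 patients act like 191.
- p = 0.30: f = 0.3477/0.4583 = 0.759, f² = 0.58; 300 act like 173.
- p = 0.15: f = 0.2332/0.3571 = 0.653, f² = 0.43; 300 act like 128.

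This step does not depend on r or n, but it does depend on the linear, normal form.

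**Step 2: power.** Power = Φ(atanh(r)·√(n−3) − 1.96), with r replaced by r·f for the cut outcome. Example with n = 300 and r = 0.20:

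- continuous: 0.2027 × 17.23 − 1.96 = 1.53, so 94%;
- 50/50 cut: r·f = 0.1596, and 0.1610 × 17.23 − 1.96 = 0.81, so 79%.

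Results for n = 300, with losses in points from unrounded values:

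| r | Continuous | 50/50 | 30/70 | 15/85 |
|---|---|---|---|---|
| 0.15 | 74% | 54% (20) | 50% (24) | 39% (35) |
| 0.20 | 94% | 79% (15) | 75% (19) | 62% (32) |
| 0.25 | 99% | 94% (6) | 91% (8) | 81% (18) |
| 0.30 | >99% | 99% (1) | 98% (2) | 93% (7) |

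At r = 0.10 both analyses are weak (41% continuous) and the loss is 13 to 21 points. For Calgary at n = 200 and r = 0.20, 81% falls to 62%, 57% and 45%. A simulation at n = 300 and r = 0.161 gave 80% continuous and 61%, 56% and 45% for the three splits, within about 1 to 1.5 points of the formula.

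**Step 3: is 15/85 a likely FEV1 split?** Section 2.1 ties its 10-15% to patients with no response in any clinical parameter. Failing one parameter must be at least as common as failing all of them. Suppose FEV1 change had an SD of 5% to 10% (assumed). Then 15% falling below the cut would need a mean gain of 5 + 1.036 × SD, or about 10% to 15%. The documents give no such gain. The 15/85 column is therefore an outer bound, not the plan's own case.

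**The case against.** The strongest defence is that the cut follows the question. The objectives are worded as the probability of response, and section 4.1 explains why partial and complete responders are pooled. If a marker separates non-responders from everyone else and is unrelated to the size of gain among responders, the efficiency calculation does not apply. A mean-change model could then be driven by differences among responders. This stands, and it is why the responder analysis should remain the stated endpoint. It does not argue against a second, continuous analysis.

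Four stronger readings are tempting and not supported:

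- A reader might infer that the plan loses 15 to 35 points of power. That range holds for r of about 0.15 to 0.20 at n = 300 under assumed alpha and splits; at r = 0.25 or 0.30 it is much smaller.
- A reader might take the roughly 15% in section 4.1 as the FEV1 failure rate. Step 3 of the working shows why it is not.
- A reader might carry the figures over to OCS and ACT. ACT is an integer score and exploratory. OCS change is not normal, and percent change is undefined for patients with no baseline maintenance dose.
- A reader might argue that measurement noise alone defeats the cut. With an assumed SD of 5% to 10%, 16% to 31% of unchanged patients would pass it by chance (1 − Φ(5/SD)). But the SD is not in the documents, section 4.1 averages values over the baseline year and over months 4 to 18, and noise also affects a continuous change score.

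It is also fair that section 6.3 plans multivariable prediction, not single-marker tests. The power figures illustrate the information lost; they do not give the performance of the planned models, and the stability of the selected marker set was not computed.

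**Conclusion.** The point holds as a cheap improvement. FEV1 is recorded as a continuous measure but analysed only in two classes, and the continuous alternative given for exacerbations is not extended to it. Under a linear, normal relation the cut keeps 58% to 64% of the information at splits from 30/70 to 50/50, and 43% at the outer bound. The matching power loss at n = 300 runs from about 35 points down to about 1 as r rises from 0.15 to 0.30. Everything except the cohort size and the cut itself is assumed, so no single figure should be attached to this plan. The documents do not support calling the responder endpoint wrong or replacing it.

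**What to change.** In the synopsis, section 3 and section 6.3, add a pre-specified analysis of change in % predicted FEV1, adjusted for baseline, using the continuous-outcome forms of the methods already named: Gaussian elastic net, regression forest and boosting. Validate it in Calgary by R-squared and calibration slope, because section 6.3 names neither. Report it beside the 5% responder analysis, which stays as the stated endpoint.

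The same addition can be made for ACT change, labelled exploratory, and for OCS dose change restricted to patients on maintenance OCS at baseline. No power gain should be claimed for either.

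The cost is wording and code; no new patients, data or visits are needed. The downside is one more analysis per endpoint and a second result on a different scale, which readers will have to reconcile with the responder result.

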1.2 SCHEMA

	Components	Year 1	Year 2
--	------------	--------	--------

AIM 1	Identify all compatible patients at University of Michigan	Blue					
	Abstract EMR data to complete database	Blue	Blue				
	Collate University of Calgary cohort with database	Blue	Blue				
	Analyze pre-treatment characteristics			Blue	Blue		
AIM 2	Process CT data to derive morphomics values		Green	Green			
	Establish morphomics phenotypes			Green			
	Assign clinical phenotypes			Green			
	Assess for overlap in phenotypes to identify novel groups			Green	Green		
AIM 3	Perform analysis using University of Michigan data					Yellow	
	Apply derived predictive variables to University of Calgary data					Yellow	
	Perform analysis					Yellow	Yellow
	Write final report					Yellow	Yellow

2 INTRODUCTION

2.1 STUDY RATIONALE

DISEASE BURDEN IN SEVERE ASTHMA AND THERAPY SELECTION

Asthma is a highly prevalent disease that affects 33 million people in the United States and Canada. The vast majority of asthma patients are well controlled with conventional asthma therapies; however, 10% of patients have severe disease that is associated with significant comorbidity and exposure to high doses of OCS. OCS use increases the odds of developing comorbid diseases such as diabetes, hypertension, cardiac disease and cataracts and is increasingly being recognized as a major contributor to severe asthma costs, making the development of alternative less harmful therapies paramount¹. Fortunately, over the past three years there has been a rapid increase in the number of biologics approved for the management of severe asthma with type II inflammation, which is estimated to be present in up to 60% of this population. The term type II inflammation refers to an increase in the levels of type II cytokines including IL4, IL5 and IL13, which induce pathologic downstream production of IgE and eosinophils. Current clinical practice utilizes surrogate biomarkers, including peripheral and sputum eosinophils, FeNO and total IgE levels, to phenotype patients with severe asthma and guide biologic drug selection. Unfortunately, these surrogates are imperfect and prone to error from multiple sources, especially in the obese².

Unequal Response to Therapy Despite Similar Biomarkers

The response to targeted biologic therapies is heterogeneous despite the use of well-studied biomarkers to select potential responders. Unfortunately, even when patients with a high likelihood of response are selected, 10-15% have complete non-response in all clinical parameters, and only 40% have a robust and complete response to therapy. This is likely related to the presence of overlapping inflammatory pathways, co-morbid eosinophilic diseases that affect response to therapy, possible sub-optimal dosing of drug and the lack of highly specific biomarkers. Precision medicine approaches to severe asthma are in their infancy and the application of complex techniques to help guide therapy are urgently needed. Currently, patients that are partial responders or non-responders to given therapies are switched between available biologics as a means of identifying the best therapy—an inefficient approach that is both time consuming and costly to patients and payers (**Figure 1**).

[figure not shown]

Figure 1: Improving patient outcomes with Precision Medicine

2.2 BACKGROUND

Innovation—Expanding on the Role of Body Composition

Nearly all research in severe asthma patients, including phase 3 trials for the current biologic therapies, has used BMI as a surrogate of body composition. Even when CT imaging has been used to better characterize body composition through relatively simplistic maneuvers such as calculation of total visceral and subcutaneous fat mass there have been no clinically usable predictive results from such analyses and no information about the role of the chest wall^{3,4}. Morphomics is a combination of high-throughput image analysis and deep learning techniques that enable the segmentation of tissues to precise detail, enabling the characterization of body composition to an unparalleled degree^{5,6}. Furthermore, the University of Michigan analytic morphomics group has an existing relational database of over 120,000 subjects that enables the generation of thousands of precise measurements, such as fat distribution, bone mineral density, and muscle density and size, and that can serve as a reference population for our asthma cohorts. This will allow for the accurate identification of extensive body composition patterns that differ from the norm utilizing an imaging population database on a scale that has never been done before.

Analytic morphomics provides actionable quantification of patient heterogeneity for precision medicine.

Precision medical intervention requires granular, precise, and actionable data at the time of treatment. Supported by rapid advances in new high-throughput technologies, “omics” data provide a unique opportunity to better understand pathophysiology and to translate research findings to clinical practice. These data enable clinicians to shift from traditional one-size-fits-all

treatment toward more targeted and precisely individualized therapies. Over the past decade, research at the University of Michigan has demonstrated that **morphomics** is the “omics” data most proximate to a patient’s ultimate health outcome (**Figure 2**).

[figure not shown]
[figure not shown]

Figure 2: Morphomics is the "omics" most proximate to treatment

Recent studies have shown that these digital biomarkers extracted by analytic morphomics provide much better quantitative understanding of morphological features of the human body^{7,8}. More importantly, morphomics has been shown to significantly and substantially improve the prediction of clinical outcome and cost in numerous patient populations^{9,10}. By providing a quantitative measure of a patient’s body compartment dimensions and composition, near the time of treatment, morphomics can deliver tailoring variables for clinical decision-making.

More recently, morphomic measurements of rib length, density, shape, and angle have allowed a level of analysis of the chest wall that has never been studied in asthma patients^{11,12,13}. Using adjacent ribs as a reference, we have then been able to measure intercostal muscle size and quality (**Figure 3**). Morphomics has previously demonstrated the role the chest wall can play in disease by linking rib angle and age to potentially explain the higher incidence of rib fractures in the elderly in motor vehicle collisions¹⁴. Since severe asthmatics typically have air trapping and are at risk for obesity, it follows that they would also have abnormal chest wall anatomy that could be mechanistically contributing to their disease in a way that could significantly impair their response to medical therapies. The specific characterization of chest wall anatomy in severe asthmatics has never been studied and represents an opportunity to identify novel biomarkers that could predict response/non-response to therapies and enrich the selection of patients in future targeted asthma studies of all levels of severity.

